2. STUDY OBJECTIVES AND OUTCOME MEASURES

Objective	Outcome Measure
Primary Objectives	
To evaluate the safety and tolerability of ITI administration of SL-172154 and to identify the maximum tolerated dose (MTD) or maximum administered dose (MAD) of SL-172154
 
Safety/tolerability outcomes include: incidence of all adverse events (AEs) and immune-related adverse events (irAE), serious adverse events (SAEs), fatal SAEs, dose limiting toxicity (DLT), AEs and irAEs leading to discontinuation, and changes in safety assessments (e.g., laboratory parameters, vital signs etc.) per National Cancer Institute Common Terminology Criteria for Adverse Events (NCI-CTCAE – version 5.0).
 
The MTD is defined based on the rate of DLTs and the MAD is the highest dose administered.

Secondary Objectives	
To select the recommended Phase 2 dose (RP2D) for SL-172154 when administered by intratumoral injection (ITI)
 
Based on review of all data collected during dose escalation and the pharmacodynamic cohort including safety, tolerability, PK, anti-tumor activity, and pharmacodynamic effects
 
To assess preliminary evidence of anti-tumor activity of SL-172154 when administered by ITI
 
Response per investigator assessment according to Response Evaluation Criteria in Solid Tumors version 1.1 (RECIST v1.1).
 
 ▪ Objective response rate (ORR) (proportion of subjects whose best response is a complete response [CR] or partial response [PR]) ▪ Time to response (TTR): time from the first dose until the first response (CR or PR, whichever is recorded first) that is subsequently confirmed ▪ Duration of response (DOR): time between first response (CR or PR, whichever is recorded first) that is subsequently confirmed and date of disease progression ▪ Change from baseline lesion diameter for injected lesion ▪ Change from baseline lesion diameter for non-injected lesion

Objective	Outcome Measure
Secondary Objectives	
To evaluate anti-drug antibodies (ADA) to SL-172154 when administered by ITI during and after treatment.	
 ▪ Number/proportion of subjects with positive ADA titer ▪ ADA duration ▪ Transient vs. persistent ADA
To characterize the pharmacokinetics (PK) of SL-172154 when administered by ITI	
 ▪ Maximum observed concentration (Cmax) and time at which the maximum concentration is observed (Tmax) and minimum observed concentration (Cmin) following single and multiple doses of SL-172154 ▪ Area under the serum concentration-time curve (AUC) ▪ Terminal elimination half-life ($t^{1/2}$), Clearance (CL) and Volume of Distribution (Vz)
Exploratory Objectives	
To assess pharmacodynamic biomarkers in blood prior to, on-treatment and following SL-172154 when administered by ITI	
Pharmacodynamic biomarkers in blood may include:
 
 ▪ Changes from baseline in cell counts and percentages of circulating immune cells such as: T cells, B cells, natural killer (NK) cells, and myeloid cells ▪ Circulating chemokine and cytokine levels
To assess pharmacodynamic biomarkers in tumor tissue prior to, on-treatment and following SL-172154 when administered by ITI	
Pharmacodynamic biomarkers in tumor tissue may include:
 
 ▪ Presence of SL-172154 in tumor tissue ▪ Changes in T cells subsets, B cells and macrophages and assessment of SL-172154 in the tumor tissue ▪ CD47 and CD40 expression ▪ Programmed cell death ligand 1 (PD-L1) expression
To estimate progression-free survival (PFS)	
 ▪ PFS: time from first dose to progression by RECIST v1.1 or death, whichever comes first

3. STUDY DESIGN

3.1 Description of Study Design

This clinical trial is an open label, multi-center, dose escalation, Phase 1 study of SL-172154 administered by ITI injection (see [SCHEMA](#)). This trial is designed to evaluate the safety, PK, anti-tumor activity and pharmacodynamic effects of SL-172154 administered by ITI on days 1, 8, 15 of a 21-day in cycle 1 and then on day 1 of each subsequent 21-day cycle (cycles ≥ 2). Subjects that are eligible for enrollment have locally advanced or metastatic squamous cell carcinomas of the head and neck or skin that are not amenable to further treatment with surgery, radiation or standard systemic therapies that are known to provide clinical benefit for their condition (Section [4](#)).

Dose Escalation

Dose escalation will utilize the modified Toxicity Probability Interval (mTPI-2) design [\[Guo, 2017\]](#) with target DLT rate of 30% for the MTD. The dose escalation decision rules are outlined in [Table 5](#) in Section [9.1](#). Subjects will be enrolled in cohorts of approximately 3 subjects into sequential dose levels of SL-172154 and evaluated for DLT (see Section [3.5](#) for Definition of DLT) during the 21-day DLT evaluation period starting from the first dose of SL-172154. At each dose level, a minimum 3-day stagger between dosing the first and second subject is required. The planned dose escalation is in half-log increments as outlined in [Table 1](#) and Section [3.4](#).

For each dose level, the minimum number of subjects evaluable for DLT (see Section [9.2.1](#) for definition of DLT evaluable subject) will be 3 unless unacceptable toxicity is observed prior to enrollment of 3 subjects (e.g., the first 2 subjects experience a DLT before the third subject enrolls). The maximum number of subjects evaluable for DLT at a dose level will be 12 (e.g., this may be reached by sequential enrollment of 4 cohorts of 3 subjects) assuming the dose decision is to stay at the current dose from the first 3 cohorts. After enrollment of 12 DLT evaluable subjects at a given dose level, a dose escalation decision will be made if ≤ 3 subjects experience a DLT (DLT rate $\leq 25\%$); and a dose de-escalation decision will be made if ≥ 4 subjects experience a DLT (DLT rate $\geq 33\%$). **Note:** Example scenarios for dose escalation per mTPI-2 dose decision rules are provided in Appendix [16.1](#).

During dose escalation, a review of available safety data for all subjects at a given dose level will be undertaken by the SMC approximately every four weeks and a decision made regarding the safety profile of that dose level.

Pharmacodynamic Cohorts

The Sponsor, in consultation with the SMC, may elect to open a pharmacodynamic cohort to obtain additional pharmacodynamic data from approximately 6 additional subjects at one or more dose levels that have completed evaluation for safety without exceeding the MTD. Subjects in the pharmacodynamic cohort must have tumor accessible and safe for biopsy from both an injected lesion and a non-injected lesion and must consent to providing paired biopsies for translational research. Subjects enrolled in the pharmacodynamic cohort will not inform dose escalation decisions but the pharmacodynamic and other data gathered from these additional subjects will inform selection of doses for further evaluation and the RP2D determination. Subjects in the

pharmacodynamic cohort will be followed per the Schedule of Assessment (SOA) table provided in Section 6.

3.2 Selection of Recommended Phase 2 Dose

Selection of the RP2D and schedule for SL-172154 will be based upon the totality of the data in subjects treated in the dose escalation and the pharmacodynamic cohorts. The totality of the data refers to safety, tolerability, PK, clinical activity, and pharmacodynamic markers consistent with the mechanism of action. Approximately 6 subjects (inclusive of the subjects enrolled in the Dose Escalation and Pharmacodynamic cohort) may be treated at the RP2D.

3.2.1 Sample Size

The planned total sample size for this study is approximately 18 subjects. This sample size assumes evaluation of approximately 12 subjects across 4 dose levels in dose escalation and approximately 6 subjects in the optional pharmacodynamic cohort. The goal is to enroll approximately 6 subjects at the potential RP2D, including subjects in dose escalation and the pharmacodynamic cohort.

3.3 Justification for Starting Dose and Schedule of SL-172154

The intratumoral starting dose for SL-172154 was determined based on MABEL principles, taking into account available preclinical pharmacology, toxicology, and pharmacokinetic data. The most sensitive *in vitro* measure of biological activity in response to SL 172154 exposure was the PBMC proliferation assay conducted in *Alstroemeria-Mosaic Virus* (AIMV) medium. The starting dose for the study is informed by key data from cynomolgus monkey toxicology studies, including identifying the NOAEL, and the PK results.

A starting dose of 0.003 mg (3 μ g) was chosen for the administration of SL-172154 to humans via ITI. Given as a total 1.5 mL injection (2 μ g/mL), this concentration, prior to distribution within tissue at the administration site, is comparable to the EC₅₀ value (1.8 μ g/mL) observed for human and cynomolgus monkey in the PBMC proliferation assay. Because SL-172154 is delivered locally to the tumor lesion, this dose/concentration is considered appropriate for this route of injection without further correction. Dose escalation will allow for identification of an optimal dose for subjects with advanced disease.

Intratumoral delivery has the potential advantage of reducing systemic toxicity by delivering drug directly to the tumor lesion. For immune-stimulating agents, intratumoral injection may also serve as an *in situ* vaccination approach. The proposal to use a flat dose (mg or μ g) is consistent with the recommendation from Marabelle *et al.* [Marabelle, 2018] for ITI of drugs with primary toxicity that is likely systemic.

Since SL-172154 will be administered directly into the tumor and is expected to remain primarily within the tumor tissue, PK modeling was not considered necessary to inform the starting dose. Rather, the starting dose is selected to match intratumoral concentrations of SL-172154 to effect concentrations (e.g., EC₂₀, EC₅₀) derived from the AIMV assay.

As a benchmark for toxicity, the NOAEL for SL-172154 administered IV to cynomolgus monkeys in a GLP toxicology study was 1 mg/kg [Report SL2020IB001]. The proposed SL-172154 starting dose of 0.003 mg (3 μ g) in a 70 kg human is 0.04 μ g/kg, and is 25,000 times lower than the NOAEL of 1 mg/kg. In monkeys, the 1 mg/kg dose administered IV corresponded with mean

Cmax and AUC_{0-last} values of 1230 ng/mL and 518 ng•h/mL on Day 1. Assuming complete bioavailability following an intratumoral dose, Cmax is expected to be 0.049 ng/mL (25,000 times lower) and thus, systemic exposure is expected to be negligible with intratumoral administration. It also should be noted that the planned starting dose for ITI (0.003 mg; 0.00004 mg/kg for a 70 kg subject) is ~2500-fold below the starting SL-172154 IV dose of 0.1 mg/kg in clinical study SL03-OHD-101, thus ensuring that systemic exposure following ITI will remain substantially below exposures observed following IV administration.

Targeting the EC₅₀ from the AIMV assay for an intratumorally administered drug is intended to provide a safe starting dose while minimizing the number of dose escalations needed to achieve a therapeutically effective dose. A starting dose based on 50% pharmacologic activity was found to be safe in 16 of 17 bispecific CD3 constructs administered IV or i.p. [\[Saber, 2017\]](#). Given the considerations outlined above, a starting dose (0.003 mg) based on EC₅₀ is expected to have a low likelihood of systemic toxicity while achieving local tumor concentrations consistent with in vitro pharmacologic response.

Justification for Schedule

The dosing schedule for the clinical trial incorporates SL-172154 administered by ITI on days 1, 8, 15 of a 21-day in cycle 1 and then on day 1 of each subsequent 21-day cycle (cycles ≥ 2). The rationale for the selected dose schedule is based on a paradigm of immune priming and immune boosting [\[Marabelle, 2018\]](#). The immune priming phase refers to SL-172154 administered by ITI on days 1, 8, 15 of a 21-day in cycle 1. Immune priming refers to stimulating a de novo immune response via the generation of a novel, antigen specific, adaptive immune response. Given that SL-172154 may have a short half-life and potentially a short duration of local bioactivity on the CD40 agonist end, it is hypothesized that an initial dose-intense induction phase of ITI is necessary for the local priming of an antitumor immune response. This schedule for immune priming is supported by the NHP data as no toxicity was observed at the day 8 dose, minimal pharmacodynamic effects were noted at this time point, and this dose may have contributed to the pharmacodynamic effect on day 15. In NHPs, multiple factors may have contributed to the onset of reactions at day 15 including ADA, complement activation, margination of lymphocytes and cytokine elevations. It is unknown if these contributing factors would be observed in humans at the doses studied and via the ITI route of administration.

The immune boosting phase refers to SL-172154 administered by ITI at day 1 of each subsequent 21-day cycle at cycle 2 and beyond. Immune boosting involves the enhancement of a pre-existing immune response against the tumor and is hypothesized to elicit a recall effect to a recent immune priming event or disinhibit a pre-existing antitumor immune response [\[Marabelle, 2018\]](#). Thus, the 3-week treatment free interval beyond day 22 is based upon 1) subject acceptability and 2) the durability of binding for SL-172154 to CD47. Furthermore, this interval may allow for pharmacodynamic effects to subside between subsequent doses and to mitigate toxicity. A more or less intensive dosing schedule may be instituted if safety and pharmacodynamic data support more or less frequent dosing of SL-172154.

3.4 Dose Escalation of SL-172154 Administered by Intratumoral Injection

Dose escalation will proceed using a flat dose and fixed volume format (see Section [6.8](#) for additional details). Dose escalation will begin at the starting dose of 0.003 mg as outlined in [Table](#)

[figure not shown]
1 below; intermediate dose levels not shown may be explored based on emerging data (e.g., safety). Dose escalation of intratumoral SL-172154 will not exceed half-log increments. The DLT assessment period is 21 days in length and encompasses the first 21-day cycle of therapy. Dose escalation will follow mTPI-2 decision rules outlined in [Table 5](#) in Section 9.1.

- Dose escalation in half-log increments ([Table 1](#))
- Schedule of administration for ITI of SL-172154: Doses administered on days 1, 8, 15 of a 21-day cycle in cycle 1 and on day 1 of each subsequent 21-day cycle, starting on cycle 2, day 1 (day 22) ([Figure 2](#)).
- Cycle length: 21 days
- DLT assessment period: 21 days of cycle 1

Table 1: Intratumoral Dose Escalation Plan for SL-172154

Dose Level	ITI Dose (mg) of SL-172154 ^a	ITI Volume of Dose
Level 1 - starting dose	0.003	1.5 mL
Level 2	0.01	1.5 mL
Level 3	0.03	1.5 mL
Level 4	0.1	1.5 mL
a) Intermediate or higher dose levels may be tested based on emerging safety and/or pharmacodynamic data. Dose escalation will not exceed half-log increments.		

Figure 2: ITI Schedule for SL-172154

3.5 Definition of Dose-Limiting Toxicity

DLTs are as defined in the bulleted points below. Toxicities will be graded as per NCI CTCAE v5. The determinate period for DLT is the first 21 days of ITI SL-172154 dosing. **Note:** AEs clearly related to disease progression or intercurrent illness are not considered DLTs. Inflammatory reactions attributable to local anti-tumor responses (e.g., severe pain) are not considered DLTs.

- Any death not clearly related to underlying disease or extraneous causes

- Any \geq Grade 4 AE
- Elevations in liver transaminases (aspartate aminotransferase [AST], alanine aminotransferase [ALT]) and/or total bilirubin:
 - In subjects who enroll with AST/ALT/total bilirubin \leq upper limit of normal (ULN); AST or ALT elevation of $>8 \times$ ULN **or** total bilirubin $> 5 \times$ ULN
 - In subjects who enroll with AST/ALT/total bilirubin $>$ ULN; AST or ALT elevation of $>8 \times$ baseline **or** total bilirubin $> 5 \times$ baseline
 - Evidence of Hy's Law (AST or ALT $> 3 \times$ ULN [or baseline*] with concurrent increase in total bilirubin $> 2 \times$ ULN [or baseline*] without evidence of cholestasis or alternative explanation such as disease progression or viral hepatitis; *ULN or baseline dependent on value at enrollment as described above.
- Any AE that requires permanent discontinuation of SL-172154
- Any Grade 3 or greater AE with the following exceptions:
 - Grade 3 fatigue lasting ≤ 7 days
 - Grade 3 anemia if not associated with clinical sequelae or not requiring transfusion of red blood cells (RBCs) within 48 hours.
 - Grade 3 or 4 neutropenia not associated with fever that improves to Grade 2 within 7 days.
 - Grade 3 or 4 lymphopenia
 - Grade 3 thrombocytopenia not associated with clinically significant bleeding and does not require medical intervention
 - Grade 3 injection-related reaction (first occurrence and in the absence of steroid prophylaxis) that resolves within 6 hours of onset with appropriate clinical management.
 - Grade 3 rigors or chills lasting < 6 hours that respond to optimum medical therapy.
 - Grade 3 fever lasting < 24 hours with or without medical therapy.
 - Grade 3 electrolyte abnormalities that are not associated with clinical signs/symptoms and are reversed with appropriate medical intervention
 - Grade 3 laboratory abnormalities that are not deemed clinically significant by the SMC.
 - Indirect/unconjugated hyperbilirubinemia without significant clinical consequences
 - Grade 3 or 4 amylase and/or lipase abnormalities that are not associated with clinical signs/symptoms or findings on imaging consistent with pancreatitis
 - Grade 3 vomiting and/or Grade 3 nausea that resolves within 72 hours with appropriate clinical management
 - Grade 3 hypertension that can be controlled (i.e., systolic BP < 140 mmHg and diastolic BP < 90 mmHg) with medical therapy.
 - Grade 3 endocrine disorder (thyroid, pituitary, hyperglycemia and/or adrenal insufficiency) that is managed with treatment with resolution of symptoms within 14 days after treatment onset.
 - Grade 3 diarrhea with no evidence of colitis that resolves within 72 hours with appropriate clinical management
 - Grade 3 skin toxicity (excluding injection-site reactions) that downgrades to Grade 2 or less within 7 days with optimal supportive care
 - Vitiligo or alopecia of any grade
- Other AEs may be considered a DLT as determined by the investigator in conjunction with the SMC.

A Grade \geq 3 AE(s) that occurs beyond the DLT period (21 days) or Grade 2 events that require continuous interruption of SL-172154 for more than 6 weeks or AEs that result in subjects not receiving at least two of the three scheduled dose of SL-172154 during the DLT assessment period may be taken into consideration when assessing the totality of the data in determining evaluability for DLT and the RP2D.

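### As worded, the Grade 3 anemia exception means that anemia with only one of clinical sequelae or red-cell transfusion within 48 hours is not an automatic DLT

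*Protocol*

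**What the plan says.** Protocol 3.5 counts any Grade 3 or higher adverse event in the 21-day window as a DLT, subject to a list of exceptions. The anemia exception reads "Grade 3 anemia if not associated with clinical sequelae or not requiring transfusion of red blood cells (RBCs) within 48 hours". The synopsis has the same sentence. The SAP uses the DLT count (sections 4, 5.1 and 8.1) but does not restate or correct the definition.

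Three other exceptions in the list also combine two conditions:

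- Thrombocytopenia: "Grade 3 thrombocytopenia not associated with clinically significant bleeding and does not require medical intervention".
- Electrolytes: "Grade 3 electrolyte abnormalities that are not associated with clinical signs/symptoms and are reversed with appropriate medical intervention".
- Amylase/lipase: "Grade 3 or 4 amylase and/or lipase abnormalities that are not associated with clinical signs/symptoms or findings on imaging consistent with pancreatitis".

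Several other provisions of 3.5 bear on an anemia case:

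- A separate criterion makes a DLT of "Any AE that requires permanent discontinuation of SL-172154".
- A discretionary item says "Other AEs may be considered a DLT as determined by the investigator in conjunction with the SMC".
- A further exception covers "Grade 3 laboratory abnormalities that are not deemed clinically significant by the SMC".
- The opening note excludes events plainly attributable to disease progression or an intercurrent illness.
- The closing paragraph says that adverse events causing a subject to miss too many cycle 1 doses "may be taken into consideration when assessing the totality of the data in determining evaluability for DLT and the RP2D".

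**The concern.** The sentence exempts Grade 3 anemia when either feature is missing. A subject transfused within 48 hours who has no sequelae is exempt, and so is a subject with sequelae who is not transfused in that time. By contrast, Grade 3 thrombocytopenia that needs medical intervention falls outside its own exception. No section explains why anemia should be treated more leniently.

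The DLT count feeds the decision table (Protocol Table 5, SAP Table 2) and the choice between reporting an MTD and a MAD (Protocol 9.2.4, SAP 8.1). Transfusion without sequelae is foreseeable. Inclusion criterion 9 admits subjects with hemoglobin just above 9.0 g/dL after five transfusion-free days, and the Grade 3 anemia guidance in 3.7.1 permits transfusion simply to restore a safe hemoglobin.

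Evaluability is also affected. Grade 3 anemia holds the drug (3.7.1). A subject held after one dose and without a DLT does not meet the two-of-three-doses limb of the DLT Evaluable definition (9.2.1) and may be replaced (9.1). If the same event were a DLT, the subject would be evaluable through the other limb. The wording can therefore change the denominator as well as the numerator.

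**Working it through.** **Step 1: the logic.** Let A be clinical sequelae and B be red-cell transfusion required within 48 hours. As written, the exemption is (not A) or (not B). Joined by *and*, it is (not A) and (not B).

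| A: sequelae | B: transfusion | Automatic DLT as written | Automatic DLT with *and* |
|---|---|---|---|
| no | no | no | no |
| no | yes | no | yes |
| yes | no | no | yes |
| yes | yes | yes | yes |

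One of four case types is an automatic DLT as written, and three of four with *and*. Two differ. Three is an upper bound for two reasons: the note excluding progression and intercurrent illness applies under either wording, and the SMC laboratory exception could still remove some cases.

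**Step 2: which reading the list supports.** Thrombocytopenia is the only true structural parallel, with two negatives joined by *and*. The electrolyte item joins a negative to a positive condition (reversal), so it is weaker evidence. The amylase/lipase item puts one negative over *or*, meaning neither. That shows the list requiring both features to be absent, but in a different grammatical form.

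**Step 3: whether other routes close the gap.** The default for Grade 3 anemia in 3.7.1 is to hold the drug, not to stop it permanently, so the discontinuation criterion is not met by default. Sequelae that are themselves non-excepted Grade 3 or higher events are DLTs in their own right. Otherwise a DLT depends on investigator/SMC discretion.

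**Step 4: what one reclassified subject does.** Inputs are the Beta(1,1) prior and 30% target (Protocol 9.1) and Table 5. With x DLTs in n subjects the posterior is Beta(1+x, 1+n−x). For n = 3, P(rate > 0.30) equals P(Bin(4, 0.3) ≤ x):

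- 0/3: 0.7^4 = 0.2401; Table 5 says escalate.
- 1/3: 0.2401 + 4 × 0.3 × 0.343 = 0.6517; stay.
- 2/3: 0.6517 + 6 × 0.09 × 0.49 = 0.9163; de-escalate.

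For an otherwise evaluable subject in a cohort of three, one more DLT turns escalate into stay, or stay into de-escalate. That is true of any single extra DLT and does not measure this wording.

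**Step 5: the MTD/MAD statement.** A MAD is reported only if the observed rate is below 25% at every level. With no other DLT in the study, one reclassified subject gives 1/3 = 33.3% or 1/4 = 25.0%, which changes the report to an MTD. With 1/5 = 20.0% or 1/6 = 16.7% it does not change.

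**Step 6: how likely such a case is.** The documents give no rate. Anemia is listed for systemically given CD47-SIRPα agents (1.4.1). Against that, the monkey GLP study found neither hemolysis nor anemia (1.2.4). The highest listed dose, 0.1 mg in a 70 kg subject, is also 1 ÷ (0.1/70) = 700 times below the 1 mg/kg NOAEL.

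Purely as an assumption, suppose the per-subject probability q of one-feature Grade 3 anemia were 5%, 10%, 20% or 30%. The chance of at least one such case among three subjects, 1 − (1 − q)^3, would be 14.3%, 27.1%, 48.8% or 65.7%. The considerations above suggest that the upper part of this range is unlikely.

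**The case against.** The best reply is that this is an ambiguity that sensible readers would resolve correctly. People often write *not A or not B* when they mean neither, and the SMC may well have applied it that way. The list also cannot be parsed strictly throughout. Any Grade 4 event is a stand-alone DLT, yet Grade 4 neutropenia, lymphopenia and amylase/lipase appear as exceptions under a different item. It therefore has to be applied partly by evident intent. Several safeguards remain (discontinuation, discretion, and consideration of missed-dose events for evaluability), and with enrollment stopped the practical effect may be nil.

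Much of this stands, and it limits the severity. It does not remove the point, because neither document says which reading governs the DLT table, the DLT listing and the MTD/MAD statement, all of which are still planned.

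A reader might infer that escalation went ahead on an undercounted DLT rate, or that the MTD/MAD conclusion is unsafe. The documents do not support that. They do not show that any Grade 3 anemia occurred, or that anyone applied the permissive reading. Nor do two discordant cells out of four mean that half of Grade 3 anemia escapes, because the cells carry no frequencies.

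**Conclusion.** The point holds as a minor drafting error in a rule that feeds the decision table and the MTD/MAD statement. As written, one case type is an automatic DLT; with *and*, up to three are. The literal logic is certain. That *and* was intended is an inference, resting mainly on the thrombocytopenia item. Any consequence for this study is unknown and probably small: it needs at least one Grade 3 anemia in the 21-day window with exactly one of the two features, not plainly due to progression or intercurrent illness, and not already a DLT by another route. SAP section 1 records that enrollment was discontinued as of 24 February 2022, so no further escalation decision in this study should depend on it. What remains is how any such case is classified and reported.

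**What to change.** For any further use of this definition, word the exception in 3.5 and the synopsis as: *Grade 3 anemia not associated with clinical sequelae and not requiring RBC transfusion within 48 hours*.

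For this study, do not silently substitute the new wording. First check whether any Grade 3 anemia occurred in the 21-day window. If none did, say so in one sentence in the SAP or study report, and the point is closed. If any did:

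- list attribution, sequelae, transfusion date, doses received and DLT-evaluable status;
- state which reading was used for escalation, where that is documented;
- report the DLT count and the MTD/MAD statement under both readings only if they differ.

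The cost is at most one short listing and a brief narrative review. The listings planned in SAP 6.8 and 6.9 give start and end dates rather than clock times, so the 48-hour limit can only be approximated. No sequelae field is described, and a transfusion may or may not have been recorded as a concomitant procedure. Protocol 14.1 requires escalation decisions to be documented but not how an exception was read, so the reading may not be recoverable. With enrollment stopped, no protocol amendment is needed.
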